INR	VA	International Normalized Ratio Test Results will be identified using Logical Observation Identifiers Names and Codes (LOINC; 34714-6, 38875-1, 46418-0, 52129-4, 5895-7, 5896-5, 61189-7, 6301-6, 72281-9) occurring anytime during the baseline period will be evaluated.
CHADS₂ Score	Both VA and Medicare	CHADS ₂ Score will be calculated according to the points algorithm outlined in Appendix Table 5 .

Variable	Data Source(s)	Operational Definition
CHA2DS₂-VASc Score	Both VA and Medicare	CHA2DS ₂ -VASc score will be calculated according to the points algorithm outlined in Appendix Table 6 .
HAS-BLED Score	Both VA and Medicare	HAS-BLED score will be calculated according to the points algorithm outlined in Appendix Table 7 .
Baseline Medication Use	Both VA and Medicare	A flag will be created for the following medications prescribed during the baseline period: angiotensin-converting enzyme inhibitors/ angiotensin-receptor blockers, aspirin, beta blockers, statins, proton pump inhibitors, H ₂ -receptor antagonists, antiplatelets, nonsteroidal anti-inflammatory drugs, inhibitors of warfarin, inducers of warfarin, dronedarone, digoxin, calcium channel blockers, renin angiotensin system antagonists, glucocorticoids, diuretics, metformin, sulfonylureas, thiazolidinedione, insulin, other diabetes drugs, antiulcer agents, and antidepressants (See Appendix Table 8 for codes).
Bariatric Surgery	Both VA and Medicare	A flag will be created for patients with claims for bariatric surgery (See Appendix Table 9 for codes).
CCI	Both VA and Medicare	Charlson Comorbidity index will be calculated as a continuous variable (See Appendix Table 10 for calculation and codes).
Comorbid Conditions	Both VA and Medicare	The following comorbid conditions will be flagged in baseline: History of stroke/SE, history of bleeding, myocardial infarction, renal disease, liver disease, dyspepsia or stomach discomfort, diabetes, hypertension, congestive heart failure, non-stroke/SE peripheral vascular disease, anemia and coagulation defects , transient ischemic attack, coronary artery disease, peripheral artery disease (See Appendix Table 11 for codes).

Table 2. Clinical and Outcome Variables

Variable	Data Source(s)	Operational Definition

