9.7.1. Analysis Plan for Primary Objective

Baseline demographic and clinical factors such as age, sex, geographic region, baseline medications, and co-morbidities among NVAf patients initiating OAC will be summarized. Descriptive statistics, (ie, mean, standard deviation, median, and inter-quartile range for continuous variables and differences across treatments) will be compared using the Student's t-test or Wilcoxon rank sum test. Percentages for categorical and binary variables will be presented for all baseline patient characteristics and will be compared using the chi-square test or Fisher's Exact test.

The cumulative incidence rate for clinical outcomes (stroke/SE, MB, net clinical benefit) will be calculated. MB will be stratified by GI bleeding, ICH, and other bleeding; Stroke/SE will be stratified by hemorrhagic, ischemic, and systemic embolism. The incidence rate will be calculated as the number of patients who experience the event divided by the observed time at risk. The incidence rate will be calculated per 100 person-years.

Inverse Probability Treatment Weighting (IPTW)

Inverse probability treatment weighting (IPTW) will be used to balance patient characteristics when comparing outcomes among different cohorts. Three sets of IPTW will be conducted (all patients, obese patients, and severely obese patients). Depending on sample size, IPTW will also be conducted for the standard dose patients separately. In addition, the primary analysis will be conducted for apixaban vs warfarin and depending on the sample size, other OAC comparisons will be conducted.

IPTW uses propensity scores to obtain estimates of the average treatment effect. The propensity score will be calculated using a logistic model with treatment cohorts included in the model, using warfarin patients as the reference (ie, control cohort). The propensity score is defined as the probability of a patient receiving a certain treatment or not conditional on their observed baseline covariates (eg, age, gender, comorbidities, medications, etc.). The list of variables included in the logistic model will be based on clinical rationale. The propensity score acts as a balancing score between the cohorts. After calculating the propensity score, the distribution of the propensity scores will be reviewed. Each patient will be weighted by the inverse of the probability of their treatment option (weight=1/propensity score).

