If a treated patient has a very low propensity score, a very large weight will be generated. Large weights can increase the variability of estimated treatment effect. In order to address this, the weights will be stabilized. In order to stabilize the weights, the treatment option and control weights will be multiplied by a constant, equal to the expected value of being in the treatment or comparison cohorts, respectively (see below). This reduces the variability of the weights and reduces the variance of the treatment effect estimates.

$$\frac{\sum_{i=1}^{N_T} PS_i}{N_T} * \frac{1}{PS_i}$$

The distribution of the stabilized weight will be reviewed. If no extreme outliers are observed, the stabilized weights will be applied to the sample. In cases of extreme outliers, the large weights could be set to a less extreme value (eg, recoding all weights that are outside 5th and 95th percentile to the 5th and 95th value, respectively). If needed, truncation can be done after stabilizing the weights.

After the weights are applied, the balance of the baseline covariates will be assessed. First, the means and proportions of baseline variables will be compared. The standardized difference compares the difference in means in units of the standard deviation. If the standardized difference is less than 10%, the covariates will be considered balanced. For continuous variables, the balance of the distribution will also be assessed. The high-order moments and interactions between variables should be similar between cohorts. The standardized difference will be used to compare the mean of the square of continuous variables. Graphical comparisons of the distribution of continuous variables will be completed. Side-by-side boxplots and empirical cumulative distribution functions will be used to compare the distribution of continuous covariates in the unweighted and weighted samples. Since the graphical approach can be subjective, a numerical method for comparing the distribution of continuous baseline covariates will also be completed.

Kolmogorov-Smirnov test allows a comparison of the distribution of a continuous variable between two independent groups.³³⁻³⁶

Cox Proportional Hazards Model

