Renin Angiotensin System Antagonists	benazepril, captopril, enalapril, fosinopril, lisinopril, moexipril, perindopril, quinapril, ramipril, trandolapril, candesartan, eprosartan, irbesartan, losartan, olmesartan, telmisartan, valsartan, azilsartan, candesartan, eprosartan, irbesartan, losartan, olmesartan, telmisartan, valsartan, eplerenone, spironolactone	
Glucocorticoids [oral and injectable]	beclomethasone, betamethasone, budesonide, cortisone, dexamethasone, hydrocortisone, methylprednisolone, prednisolone, prednisone, triamcinolone	
Diuretics	acetazolamide, methazolamide, bumetanide, ethacrynic acid, torsemide, furosemide, pamabrom, eplerenone, triamterene, spironolactone, amiloride, indapamide, hydrochlorothiazide, chlorthalidone, metolazone, methyclothiazide, bendroflumethiazide, polythiazide	
Metformin	Metformin	
Sulfonylureas	acetohexamide, chlorpropamide, glimepiride, glipizide, glyburide, tolazamide, tolbutamide	
Thiazolidinedione	pioglitazone, rosiglitazone	
Insulin	insulin	

Mechanism of Action	Drug
Other Diabetes Drugs	exenatide, liraglutide, dulaglutide, repaglinide, sitagliptin, saxagliptin, linagliptin, alogliptin, nateglinide, acarbose, miglitol, canagliflozin, dapagliflozin, empagliflozin, pramlintide
Antiulcer Agents	nizatidine, sucralfate, misoprostol, famotidine, omeprazole, cimetidine, ranitidine hydrochloride, Dexlansoprazole, Esomeprazole, Lansoprazole, Omeprazole, Pantoprazole, Rabeprazole, Burimamide, Ebrotidine, Metiamide, Cisapride, Pirenzepine, Propantheline, Roxatidine acetate
Antidepressant	citalopram, escitalopram, paroxetine, fluoxetine, fluvoxamine, sertraline, desvenlafaxine, duloxetine, levomilnacipran, milnacipran, venlafaxine, vilazodone, vortioxetine, nefazodone, trazodone, reboxetine, teniloxazine, viloxazine, bupropion, amitriptyline, amitriptylinoxide, clomipramine, desipramine, dibenzepin, dimetacrine, dosulepin, doxepin, imipramine, lofepramine, melitracen, nitroxazepine, nortriptyline, noxiptiline, opipramol, pipofezine, protriptyline, trimipramine, amoxapine, maprotiline, mianserin, mirtazapine, setiptiline, isocarboxazid, phenelzine, tranylcypramine, selegiline, caroxazone, metralindole, moclobemide, pirlindole, toloxatone, bifemelane, amisulpride, lurasidone, quetiapine, aripiprazole, brexpiprazole, lurasidone, olanzapine, quetiapine, risperidone, lithium

Table 9. Bariatric Surgery Codes

Type	Codes	Description

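### The antidepressant flag is defined by a drug list that includes seven antipsychotics and lithium, so its label does not match what it counts

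*Combined protocol and SAP*

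**What the plan says.** Section 9.3, Table 1, sets up the baseline medication variables: "A flag will be created for the following medications prescribed during the baseline period". The list of groups ends with "other diabetes drugs, antiulcer agents, and antidepressants", and the entry sends the reader to Appendix Table 8 for the definitions.

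In section 17.1, the Table 8 antidepressant row opens with a long list of antidepressants of several classes. It closes with "amisulpride, lurasidone, quetiapine, aripiprazole, brexpiprazole, lurasidone, olanzapine, quetiapine, risperidone, lithium".

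Section 9.7.1 gives the uses of the baseline medication variables:

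- Description: "Baseline demographic and clinical factors such as age, sex, geographic region, baseline medications, and co-morbidities among NVAf patients initiating OAC will be summarized", with cohorts then compared. This serves Aim 1, one of the primary objectives in section 8.1.1.
- Propensity score: treatment probability is modelled "conditional on their observed baseline covariates (eg, age, gender, comorbidities, medications, etc". The choice of covariates is left open: "The list of variables included in the logistic model will be based on clinical rationale".
- Balance: "After the weights are applied, the balance of the baseline covariates will be assessed". A standardized difference below 10% counts as balanced.

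**The concern.** The label and the definition disagree. Table 1 asks for antidepressant use, but the row that a programmer would code from also collects antipsychotics and lithium. Someone treated with olanzapine for psychosis or lithium for bipolar disorder, with no antidepressant prescription, would be reported as an antidepressant user.

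Two things are at stake. The first is the accuracy of one line in the baseline tables that report Aim 1. The second is conditional: if the flag is among the propensity-score covariates, the weighting and the balance check would act on a mixture of two drug groups, and a satisfactory result for the mixture would say little about either part.

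**Working it through.** The plan states no figure for this flag, so there is nothing to reproduce. The check is a count of the row, a comparison of the places where these drugs could otherwise be handled, and a short argument on direction.

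**Count of the Table 8 row**

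| Part of the row | Entries | Distinct drugs |
|---|---|---|
| Whole row | 62 | 60 |
| Closing run (quoted above) | 10 | 8 |
| Remainder | 62 − 10 = 52 | 60 − 8 = 52 |

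The eight distinct drugs in the closing run are seven antipsychotics (in alphabetical order: amisulpride, aripiprazole, brexpiprazole, lurasidone, olanzapine, quetiapine, risperidone) and lithium. The two surplus entries are the repeats of lurasidone and quetiapine. The documents do not state drug classes; this classification is standard pharmacology.

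**Does anything else in the plan deal with it?**

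- Table 8 carries no condition that these drugs count only with an antidepressant or with a depression diagnosis.
- Neither Table 1 nor Table 8 has an antipsychotic, mood-stabilizer or lithium group, and none of the eight drugs appears in another Table 8 row.
- The comorbidities in Table 1 and Table 11 include no depression, bipolar or psychosis flag, so no other planned variable separates these patients.

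**Direction**

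Let p be the proportion with at least one captured prescription for the 52 antidepressants. Let q be the proportion, among everyone else, with a captured prescription for any of the eight other drugs.

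- Flag as written: p + (1 − p)q
- Antidepressant use: p
- Excess: (1 − p)q, which cannot be negative

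The flag therefore equals or exceeds antidepressant use whatever the data show.

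**Size**

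The documents give neither p nor q, so the excess cannot be computed from them. Purely as an illustration, assume p between 15% and 35% and q between 0.5% and 5%. The share of flagged patients with no antidepressant is (1 − p)q / [p + (1 − p)q]:

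- Low end (p = 0.35, q = 0.005): 0.65 × 0.005 = 0.00325; 0.00325 / 0.35325 = 0.009, about 1%.
- High end (p = 0.15, q = 0.05): 0.85 × 0.05 = 0.0425; 0.0425 / 0.1925 = 0.221, about 22%.

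The width of that range shows only that the answer depends on the assumptions.

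**Balance**

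Write p and r = (1 − p)q separately for apixaban and warfarin. The standardized difference for the flag depends on p + r in each cohort. The two sums can agree while a higher p in one cohort is offset by a higher r in the other. Balance on the flag therefore does not imply balance on either component. This matters only if the flag is a model covariate or is the sole check on these drugs.

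**The case against.** The best defence is that the grouping is deliberate. Several of these drugs are also used to augment antidepressants, the run is a short selection and not a full antipsychotic list, and Table 8 contains other broad or overlapping groups. For example, spironolactone and eplerenone sit under both the renin-angiotensin row and the diuretics row, and the antiulcer row repeats acid-suppressing drugs listed elsewhere. On that reading the fault is an imprecise label.

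Intent cannot be excluded, but it does not remove the mismatch. A patient on an augmenting drug plus an antidepressant, with both prescriptions captured, is already flagged by the antidepressant. Adding the eight drugs changes the flag only for patients with no captured antidepressant. Some of those may be treated for depression, but the row takes them all, whatever the indication. If the wider group is wanted, the name must say so.

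Three further objections stand and limit the point:

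- A reader might infer that the cohorts will be balanced on this flag. The plan does not say so. Section 9.7.1 names medications only as an example and leaves the list to clinical judgement; the matching covariates in section 9.7.2 do not name medications and are also left open.
- A reader might infer that the flag stands for serotonergic exposure, and so for bleeding risk. The plan gives no such rationale, and the row also lists bupropion and reboxetine, so it would not isolate that exposure even after correction.
- Simply deleting the eight drugs would discard the only baseline record of their use.

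**Conclusion.** The point holds as a mismatch between label and definition. Applied literally, the Table 8 row counts patients with none of its 52 antidepressants as antidepressant users, so the reported percentage equals or exceeds captured antidepressant use. That direction needs no assumption beyond the usual classification of the eight drugs. The size is unknown: the illustrative 1% to 22% of flagged patients rests wholly on assumed prevalences.

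If the flag enters the propensity model, which is likely but not stated, balance on it would not guarantee balance on antidepressants or on the other eight drugs.

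The tempting stronger reading is that the comparison of apixaban with warfarin is biased. The documents do not support it. Such bias would require use of the component drugs to differ between cohorts and to relate to outcome, and neither is shown. This is one of more than 20 medication flags. It plays no part in eligibility, exposure, outcomes, CHADS₂, CHA₂DS₂-VASc, HAS-BLED or the Charlson index. The issue is minor, worth correcting because it changes a reported number at almost no cost.

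**What to change.** Split the Table 8 row into two: an antidepressants flag holding the 52 drugs that remain once the closing run is taken out, and an antipsychotics/lithium flag holding the eight. Remove the duplicate entries for lurasidone and quetiapine, and add the new flag to the Table 1 list. This keeps all the baseline information and lets each group be reported and, if chosen, modelled and checked for balance separately.

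If the pooled group was intended, keep it, state that in the protocol, and relabel the flag so that the baseline tables name antipsychotics and lithium as well as antidepressants.

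Either change is an edit to one codelist row and is best made before the baseline tables are run. It fits the clinical review of the coding strategy promised in section 9.8. The only downside of the split is one extra baseline flag.
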